7.1 Sample Size and Power Determination

For cluster-randomized designs, clinic is the unit of randomization and the unit of analysis is the individual. Power is reduced by variability among clinics, represented by the intra-class correlation (ICC), analogous to an R-squared. The size of the individual sample affects precision within clusters and certain outcomes are less susceptible to potential confounding vs. others (e.g., smoking rates vs. provider adherence) since they are more independent.

For Aim 1, the analysis will compare ATTOC to UC on weeks 36 (EOT) and 52 rates of adherence to guidelines for treating TUD. The sample size was determined by assessing the mean change in practice behavior detected in Guldish et al. [18]. Given the expectation from that trial that the UC mean level of practice will be 2.36 (SD=.87), the present sample of N=14 agencies (with 280 subjects) provides 80% power ($\alpha=.05$) to detect an effect if practice behavior increases by 0.32 (on a 5-point scale) if the ICC is 0. But if our ICC is .05, .10, or as high as .15, we have 80% power ($\alpha=.05$) to detect a difference between ATTOC and UC of 0.44, 0.54, and 0.62, respectively. If 15% of the personnel are lost-to-follow-up, we will have 80% power ($\alpha=.05$) to detect an effect if practice behavior increases by 0.34 for ICC=0, by 0.46 for ICC=.05, by 0.56 if ICC=0.10, and by 0.63 if ICC=.15. The effects of ATTOC were stronger at the 3-month follow-up (mean change of 0.51), vs. EOT [18], so the current power is adequate for both time-points. Likewise, because the client sample will be more than twice as large as the clinic staff sample, we will have greater than 80% power to detect differences using the measure of physician adherence collected from clients.

For Aim 2, the analysis will compare the rates of smoking cessation between the ATTOC intervention and UC at weeks 36 and 52. We can expect that UC cessation rate will be < 2% [18]. With 14 sites (n=700 clients, ITT), we have 80% power ($\alpha=.05$) to detect a difference between ATTOC and UC of 4% with an ICC=0. But if our ICC is .05, .10, or as high as .15, we have 80% power ($\alpha=.05$) to detect a difference between ATTOC and UC of 10%, 15%, and 19%, respectively, with 14 sites and n=700 client (ITT).

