For Aim 3, the analysis will use non-inferiority testing to compare mental health and QOL across ATTOC and UC at weeks 36 and 52. Standard statistical tests, which may yield a non-significant comparison of means or proportions, cannot be used to claim that the treatments are equal since "the absence of evidence is not evidence of absence". Among persons with SMI, the rate of psychiatric hospitalization nationally is 11.4% [114], which may represent UC (i.e., 88.6% of UC subjects will not have a hospitalization across the 52 weeks). One study found that 3.3% of clients with an SMI treated for TUD had a psychiatric hospitalization [48] or that 96.7% of clients treated for TUD did not experience a psychiatric hospitalization. We assume 14 sites (700 clients), with potential loss of 15% to follow-up, and assume approximately 90% non-hospitalization in the UC group. We will set our non-inferiority floor 20% below the US rate, which yields 80% power to detect non-inferiority if the ICC is as much as 0.15 (more power if ICC is less than 0.015).

A trial with smokers with an SMI reported baseline BASIS-R scores of 2.1 (SD=0.8) and SF-12 scores of 48.7 (SD=12.5) for the physical sub-scale and 27.8 (SD=12.9) for the mental sub-scale, which estimates UC [107]. Given the sample of 14 sites (700

clients) and potential 15% loss to follow-up, we have 80% power ($\alpha=0.05$) to detect non-inferiority if the results for the ATTOC arm differ from UC by as much as 0.19 on the BASIS-R, when ICC=0, and by 0.50 when ICC=0.15.

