7.2 Statistical Methods

We will assess sample characteristics by treatment arm and site with chi-square or regression. These variables will also be examined for their relationship to completion of outcomes. Variables related to treatment arm or completion of follow-ups ($p < .10$) may be covariates in analyses. Fidelity and adherence measures will be evaluated across treatment arms, and the measures can be included in primary analyses. We will examine if the rate of missing data is related to a range of variables using chi-square and regression and use appropriate methods for dealing with missing data (e.g., [115]). Analyses will assume that all subjects for whom smoking outcome data are unavailable are smokers (ITT) but we can also conduct a "completers-only" analysis. Because this is a cluster-randomized trial, the observations within a cluster cannot be considered totally independent. Variation among clusters may be confounded with treatment because clusters are nested within treatment. We will account for this clustering using hierarchical linear models (mixed models), estimating separate variance components for random site effects within treatment. Lastly, since we cannot guarantee that clinicians will be blind to their clients enrolling in this study, we will include a statement in personnel consent forms asking that they refrain from asking their clients if they are enrolled in the study.

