7.2.1 Analysis of Outcomes of Interest

The effects of the ATTOC model on provider adherence to guidelines for treating TUD: We hypothesize that the ATTOC intervention will increase adherence to guidelines for treating TUD vs. UC. The outcome is continuous and the hypothesis will be tested by a treatment arm term in a mixed-models linear regression model that may include covariates. Mixed models may account for individual level clustering inherent in longitudinal studies and site level clustering. Outcomes of the analysis will be characterized by regression coefficients and confidence intervals. Significance will be determined from a z-score corresponding to the treatment variable. Although level of adherence at 36 and 52 weeks will represent our primary outcome variables, similar regression analyses will be performed for assessments at Weeks 12 and 24. Also, we can examine models of specific clinician practices (e.g., identifying smoking, recommending pharmacotherapy) and examine adherence from the client perspective and based on adherence data ascertained from the EHR.

The effects of the ATTOC model on client smoking: The hypothesized effect of treatment arm (i.e., the difference in quit rates between subjects receiving the ATTOC intervention or UC) will be tested by a treatment arm term in a mixed-models logistic regression model with covariates. Outcomes of the analyses will be characterized by odds ratios (e.g., odds of quitting smoking) and 95% confidence intervals. Although quit-rates at the end of 36 and 52 weeks will represent our primary outcomes, similar analyses will be performed for other assessments of quit rates (e.g., at Weeks 12 and 24). In addition, as many participants will fail to become abstinent, we will explore the use of zero-truncated negative binomial regression for count data to examine the main effects of treatment arm on changes in smoking rate at all assessment time-points.

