The effects of the ATTOC model on client mental health functioning and QOL: We will compare treatment arms in terms of the frequency of hospitalizations (binary) and mental functioning evaluations (continuous) over 52 weeks. Again, we will use mixed models to account for clustering, while accommodating either the binary outcome with logistic regression or the continuous measures with linear regression. Equivalence uses two one-sided tests against lower and upper equivalence bounds. The null hypothesis is that the groups are not equivalent and are determined to be equivalent when the mean or proportion is significantly different from both boundaries. We will use this approach to determine whether hospitalization rates are higher (null) in the ATTOC group or equivalent, and whether mental functioning is lower in the ATTOC group (the null) or equivalent. All hypotheses will be tested at $\alpha=0.05$ (0.025 for any one sided non-inferiority test).

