The cost-effectiveness of the ATTOC program vs. UC: We will compare the societal cost (i.e., the sum of all measured categories of costs, including treatment and indirect costs) and effects of ATTOC vs. UC. If one treatment is found to be more costly and more effective, there is a trade-off between the additional effectiveness and additional resources needed to achieve those outcomes. This trade-off is represented by the incremental cost-effectiveness ratio (ICER), which is a ratio of the difference between mean costs in each treatment group and the difference between the cessation rates across treatment arms at weeks 36 and 52. This ratio will represent the additional cost of ATTOC vs. UC to produce an additional quitter. The quit rate outcome measure is used in our primary measure of cost-effectiveness because it is measured directly and because it can be compared against economic evaluations of other smoking interventions. Hypothesis testing for an ICER involves determining whether the ICER is significantly $<$ the maximum acceptable ICER. Unfortunately, the maximum willingness to pay for a quit is unknown. However, \$50,000 is accepted as a maximum ICER for the outcome of cost/life year saved, but wide bands around this value are common. This outcome looks at cost-effectiveness of the intervention over a lifetime. Because this is a relatively brief trial we will use a simulation-based analysis to project effects of quitting into long-term mortality and costs [116], employing standard assumptions and parameters [117]. Because this projection is based on parameters that have wide ranges, we will conduct a sensitivity analysis to assess the sensitivity of our estimates of costs and cost-effectiveness to the speculative nature of some of the values used in the analysis. We will consider how cost-effectiveness may change with different: 1) costs of treatment; 2) methods to handle attrition of cost data; and 3) ceiling ratios. Because of the poor statistical properties of the ICER as with ratios [118], we will transform the ratio into incremental net monetary benefits (INMB) with the following: $[L \cdot E] - C$ where L =ceiling ratio, E =difference in mean effects, and C =difference in mean costs. The hypothesis test that the ICER is $<$ the ceiling ratio is equivalent to the hypothesis test that the INMB is >0 . The INMB standard error is estimated with the formula in Willan [119] and amounts to the typical statistical formula for standard error. The hypothesis is that the ICER will be cost effective if the

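### The INMB standard error names no clinic term and must be reconciled with the clustering rule in section 7.2; the ordinary formula applied to clients gives too narrow an interval whenever net benefit varies by clinic

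*Combined protocol and SAP*

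**What the plan says.** Section 4.1 randomizes 14 clinics, 7 per arm, and section 5.2 plans about 50 clients per clinic. Section 7.2 gives the general rule: "We will account for this clustering using hierarchical linear models (mixed models", with random site effects within treatment.

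Section 7.2.1 then takes the aims in turn.
- **Aim 1:** "the hypothesis will be tested by a treatment arm term in a mixed-models linear regression model". It adds only that mixed models may deal with site-level clustering.
- **Aim 2:** a mixed-models logistic regression is named, without mention of clinic or site.
- **Aim 3:** "Again, we will use mixed models to account for clustering".
- **Cost-effectiveness:** no mixed model is named. The INMB is defined as the ceiling ratio times the difference in mean effects, minus the difference in mean costs. Its standard error comes from a cited formula and "amounts to the typical statistical formula for standard error".

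The secondary aim is called cost-effective if the INMB for cost per life-year is above 0 at the 0.05 level; a second rule asks that its confidence interval exclude 0. Life-years come from projection: "we will use a simulation-based analysis to project effects of quitting into long-term mortality and costs". Cost per quitter is the lead measure ("The quit rate outcome measure is used in our primary measure of cost-effectiveness"), but the plan states no ceiling or test for it.

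**The concern.** The INMB test is the only significance test stated for the secondary aim. Its effect term is projected from quitting, so clinic-to-clinic variation in quitting carries into the INMB, as does any such variation in cost. A specific instruction that describes the standard error as the usual one, placed after a general rule about mixed models, leaves two routes open. An analyst who follows the specific sentence alone would treat some 700 clients as independent although only 14 units were randomized. The interval would then be too narrow, and ATTOC could be declared cost-effective too readily. The planned sensitivity analyses vary treatment costs, the handling of missing cost data and the ceiling ratio; none of them would show this.

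**Working it through.** **Inputs from the protocol.** 7 clinics per arm (4.1); about 50 clients per clinic, so 350 per arm (5.2); up to 15% loss, so 0.85 × 50 = 42.5 per clinic (6.4 and 7.1); ICCs of 0, .05, .10 and .15 for quitting and 0 and .15 for BASIS-R (7.1).

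**Assumptions.** No ICC is given for cost or INMB; I take 0 to .15 and add .01 and .02. I read the test as two-sided 5%, which gives 2.5% nominal for a claim of INMB > 0. Clinics are of equal size and no credit is taken for matching.

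**Step 1: the plan's own figures.** Design effect: DE = 1 + (m − 1) × ICC.
- **Aim 2:** effective n per arm = 350/DE, usual-care quit rate 2%, 80% power, two-sided 5%, pooled variance. The detectable differences come to 4.2%, 10.0%, 14.9% and 19.4% at ICC 0, .05, .10 and .15. The plan states 4%, 10%, 15% and 19%, beginning "to detect a difference between ATTOC and UC of 4% with an ICC=0".
- **BASIS-R:** SD 0.8 and m = 42.5 give (1.96 + 0.84) × 0.8 × √(2/(7 × 42.5)) = 0.184 at ICC 0. Multiplying by √(1 + 41.5 × .15) = 2.69 gives 0.494 at ICC .15. The plan says that results may "differ from UC by as much as 0.19 on the BASIS-R, when ICC=0, and by 0.50 when ICC=0.15". Its ratio is 0.50/0.19 = 2.63; rounding of the two figures allows 2.54 to 2.73.

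So the plan's client-level power figures already contain this design effect.

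**Step 2: the ordinary standard error applied to clients.** At true INMB = 0 the test statistic has standard deviation √DE instead of 1, so

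P(false claim of INMB > 0) = 1 − Φ(1.96/√DE), and coverage of the 95% interval = 2Φ(1.96/√DE) − 1.

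| ICC (m = 50) | DE | √DE | False claim | Coverage |
|---|---|---|---|---|
| 0 | 1.00 | 1.00 | 2.5% | 95% |
| .01 | 1.49 | 1.22 | 5.4% | 89% |
| .02 | 1.98 | 1.41 | 8.2% | 84% |
| .05 | 3.45 | 1.86 | 14.6% | 71% |
| .10 | 5.90 | 2.43 | 21.0% | 58% |
| .15 | 8.35 | 2.89 | 24.9% | 50% |

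With 42.5 clients per clinic, the false-claim rates at ICC .05, .10 and .15 are 13.2%, 19.4% and 23.3%. If the 0.05 level is read as one-sided, the range for m = 50 is 5.0% at ICC 0 to 28.5% at .15.

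**Step 3: simulation checks.** Normal outcomes, 20,000 trials per ICC, give 2.4%, 14.9%, 21.0% and 25.0% at ICC 0, .05, .10 and .15. Skewed net benefit gives 2.5%, 14.8%, 21.1% and 25.3%. Rare quitting (beta-binomial, 2%) runs from about 2.6% at ICC 0 to 23% at .15.

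**Step 4: with clinic in the variance.** A t test of 7 against 7 clinic means on 12 df gives 2.4%, 2.8%, 2.4% and 2.4% in the normal simulation. A normal reference on clinic means gives P(t₁₂ > 1.96) = 3.7%. A percentile bootstrap that resamples 7 clinics per arm gives about 4.7%.

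**Step 5: width of the corrected interval.** √DE × 2.179/1.96 = 1.11, 2.06, 2.70 and 3.21 times the ordinary width at ICC 0, .05, .10 and .15.

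**The case against.** The strongest reply is that section 7.2 already covers this. The cost-effectiveness paragraph sits beneath it, and its clustering rule is not limited to any aim. A usual formula for the standard error of a net benefit can simply mean the one built from the variance of the effect, the variance of the cost and their covariance, and those could come from mixed models. The cited formula cannot be inspected. This stands: a reader might infer that the plan has decided to ignore clustering, and the documents do not support that. What remains is that the paragraph describes the formula as the ordinary one and says nothing about clinic, so the outcome depends on which sentence the analyst follows.

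It is also fair that the contrast with the other aims is limited. Only the Aim 3 paragraph commits outright to modelling clustering; Aim 1 says that mixed models may do so, and Aim 2 names the model without mentioning clinic. Silence in one more paragraph is therefore weak evidence of intent.

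A reader might take 25% as the expected error rate. The documents do not support that either. An ICC of .15 is the upper end of a range given for other outcomes. At a 2% quit rate it implies a between-clinic SD of √(.15 × .02 × .98) = 5.4 percentage points, 2.7 times the mean. The BASIS-R ratio likewise shows what the design effect does at an assumed ICC; it does not measure the ICC of INMB. But the problem does not need .15: an ICC of .01 already doubles the nominal 2.5%.

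Finally, projected life-years are not a simple client outcome. The rare-quitting check shows nearly the same inflation, so this does not remove the point, although uncertainty in the projection model is not included.

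**Conclusion.** The concern holds as a gap that has to be reconciled, not as a demonstrated error in the planned analysis. If the ordinary formula is applied to clients, the interval is too narrow for any ICC above 0. The false-claim rate at true INMB = 0 is then 5-8% at ICC .01-.02 and 15-25% at ICC .05-.15, against 2.5% nominal. These figures rest on an assumed ICC, a two-sided reading of the test, equal clinic sizes and no gain from matching. Unequal sizes would raise them and effective matching would lower them. The point affects the one stated test of a secondary aim. Aims 1 to 3 are untouched, and so is the cost-per-quitter estimate itself. It should be fixed because the test has no other safeguard and the change is small.

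**What to change.** Replace the standard-error sentence in the cost-effectiveness paragraph of section 7.2.1 with an INMB estimate and interval that account for clinic, and refer back to section 7.2. Suitable choices are a clinic-level analysis, a mixed model on client net benefit with a random clinic effect, or a joint mixed model for cost and effect with random clinic effects. Make a small-sample reference of about 12 df (14 clinics minus 2 arms) part of the rule. Do not rely on a normal reference alone or on a percentile bootstrap of 7 clinics per arm: they leave about 3.7% and 4.7% against 2.5%.

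State the confidence level in the same edit. The second decision rule could also say that the lower limit must lie above 0; this is minor, because the sentence before it already gives the direction.

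The cost is SAP wording and slightly more analysis, with no new data. The interval widens to about 1.1 times the ordinary one at ICC 0, and 2.1, 2.7 and 3.2 times at ICC .05, .10 and .15, so a claim of cost-effectiveness becomes harder to reach.

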3.2 Secondary and Exploratory Objectives

[figure not shown]
- Secondary Aim: To assess the cost-effectiveness of the ATTOC intervention. Hypothesis: ATTOC will have a favorable incremental cost-effectiveness ratio measured as dollars/quitter and dollars/life-year saved.
- Exploratory Aim 1: We will assess changes in cultural and systemic barriers to treatment as mediators of the effects of the ATTOC model on provider adherence to guidelines for treating TUD and client smoking.
- Exploratory Aim 2: To inform model dissemination, we will identify components of the ATTOC intervention that predict greater change in provider adherence to guidelines for treating TUD and client smoking.

4 Investigational Plan

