- **Smoking Knowledge, Attitudes, and Practices (S-KAP):** This survey is composed of 5 scales that assess systemic and cultural barriers to smoking cessation. These scales measure clinician practices, knowledge regarding smoking risks, barriers, attitudes and efficacy [103]. Systemic barriers include provider: 1) access to resources to treat TUD; 2) level of knowledge to treat TUD; 3) implementation of smoking cessation policies such as a smoke-free campus; and 4) use of the EHR to document and track client smoking and treatment. Cultural barriers include provider beliefs about: client interest in smoking cessation, client ability to quit smoking, client ability to understand the benefits of smoking cessation, client mental health consequences from cessation, and smoking cessation treatment being their responsibility. These Likert-type measures are sensitive to change following implementation of ATTOC [18] and have good psychometric qualities [94, 103]. This survey will also be used to measure outcomes data (items measuring the rate of: asking clients about smoking, advising them to quit, providing assistance with quitting, and arranging visits to track progress; a total adherence score can be calculated [18].)
- **Smoking Knowledge, Attitudes, and Services (S-KAS):** This survey is essentially a client version of the S-KAP and will be used to measure systemic and cultural barriers to smoking cessation from the client's perspective. The survey

contains 4 Likert-type scales that measure client knowledge regarding smoking risks, attitudes about quitting smoking as related to the clinic setting, and assessments of clinician and program services, respectively [105].

Treatment Data:

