- Lastly, assistance with the establishment of a tobacco-free workplace and campus is initiated if that is an organizational goal. This involves setting a date for campus change, including development of staff communications, appropriate signage, treatment support, and trouble-shooting potential obstacles. Some agencies may choose to restrict use to an isolated campus location.

6.2.3 Weeks 4 and 8

Usual Care (UC): No study procedures are completed.

ATTOC Intervention: Sessions at Weeks 4 and 8 are provided via video-conference (or teleconference) to continue training activities initiated in Week 1 and address concerns, obstacles, or problems that have emerged during implementation. Agency staff is provided with access to an interactive web-site administered by [name], which provides information, tools, and materials for training and treatment. Site tobacco champions are instructed in using the “dashboard” assessment of clinician and agency performance, relative to benchmarks, in order to provide formal performance feedback.

6.2.4 Week 12

Usual Care (UC): Participants complete assessments. Clinic personnel will complete the S-KAP and clients will complete the S-KAS, which allow for exploratory mediation analyses. These ~30 minute assessments will be conducted in person at the sites by the trained study staff.

ATTOC Intervention: This 2-day on-site visit to conduct a follow-up Environmental Scan evaluates early changes in outcomes and provides further training and technical assistance. During this visit, dashboard data are used to provide performance feedback to site personnel. The feedback: 1) reviews the change and communication plans, including the benchmarks for adherence to TUD treatment guidelines; 2) presents a graphical display of clinician adherence to treatment guidelines; and 3) offers coaching for clinicians with unacceptable adherence and positive reinforcement to clinicians with acceptable adherence. Data support performance feedback for improving clinician use of evidence-based treatment [99], even for TUD [100], but this will be the first time this technique is used to address TUD treatment in community mental healthcare. Participants will also complete assessments. Clinic personnel will complete the S-KAP and clients will complete the S-KAS, which allow for exploratory mediation analyses. These ~30 minute assessments will be conducted in person at the sites by the trained study staff.

6.2.5 Weeks 16 through 52

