
INMB expression of cost/life year saved is >0 at an $\alpha < 0.05$. We will also judge the cost-effectiveness ratio as being acceptable if the confidence interval for the INMB excludes 0.

Exploratory Aims: The effects of treatment arm on potential mediators (barriers) will be assessed using linear regression-based structural equation modeling (SEM). It is hypothesized that treatment arm will yield significant differences in proposed mediators which will predict week 36 and 52 quit rates and adherence to treatment guidelines. We will examine changes in mediators from baseline to week 8. After first demonstrating that treatment arm affects adherence and quit rates (Aims 1 and 2), these effects will be partitioned into mediated and unmediated effects, via path analysis and SEM. Specific hypotheses will be tested by using chi-square difference tests that contrast the overall fit of this full model with more parsimonious nested models in which specific predictive effects are fixed to zero (e.g., an unmediated path). Model goodness-of-fit indices will be contrasted to guide interpretation of results and determine the practical significance of statistically significant differences. Modification indices will be examined to guide model interpretation and modification and binary and continuous variables can be handled by Stata. This approach allows us, in principle, to test whether treatment effects on Aim 1 and 2 outcomes are due to specific mechanisms (e.g., reduction in barriers).

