9.2 Sources of Research Material

- Questionnaires assessing demographic characteristics, smoking history and behaviors, nicotine dependence (among smokers) among personnel and clients; employment characteristics (e.g., type of position, duration at agency) among personnel; System and cultural barriers to the provision of nicotine dependence treatment (among personnel); Fidelity measures to assess implementation of the ATTOC intervention (among personnel); Questionnaire assessments of client mental health and QOL
- Past and current psychiatric diagnoses, including duration of illness and frequency of hospitalizations, and compliance with agency appointments (among clients) is collected by self-report. Diagnosis and hospitalization information is verified via data requested from CBH
- Prescription data is requested from CBH (clients)
- Treatment metric data entered by ATTOC personnel participants via online "Dashboard"
- Change Plans documentation and progress notes and ATTOC consultant environmental scan visual surveying
- Self-reported smoking behavior is bio-verified with CO samples using Vitalograph CO monitors (clients)

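### Exploratory Aim 1 partitions effects only after Aims 1 and 2 succeed, so the indirect effect may never be estimated; its SEM also names no clinic level, and a staff-barrier-to-client-quit path has only 14 points.

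*Combined protocol and SAP*

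**What the plan says.** Section 3.2 sets out Exploratory Aim 1: changes in cultural and systemic barriers are to be studied as "mediators of the effects of the ATTOC model on provider adherence to guidelines for treating TUD and client smoking".

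Section 7.2.1 gives the analysis in three parts.

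- Arm on barriers, with no condition attached: "The effects of treatment arm on potential mediators (barriers) will be assessed using linear regression-based structural equation modeling (SEM").
- The hypothesis: "treatment arm will yield significant differences in proposed mediators which will predict week 36 and 52 quit rates and adherence to treatment guidelines".
- The partition, which is conditional: "After first demonstrating that treatment arm affects adherence and quit rates (Aims 1 and 2), these effects will be partitioned into mediated and unmediated effects".

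Nested models are then compared by chi-square difference tests, and mediator change is taken from baseline to week 8. The paragraph names no multilevel form, aggregation rule or cluster-robust error. Section 7.2 does promise mixed models with random site effects for the trial in general.

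Barriers are measured on two groups. For staff, Section 9.2 lists "System and cultural barriers to the provision of nicotine dependence treatment (among personnel"), collected with the S-KAP. For clients, Section 4.7 lists the S-KAS under mediators: "This survey is essentially a client version of the S-KAP and will be used to measure systemic and cultural barriers to smoking cessation". Section 6.2.4 confirms that both serve this aim: "Clinic personnel will complete the S-KAP and clients will complete the S-KAS, which allow for exploratory mediation analyses".

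**The concern.** There are two separate problems.

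The first is the condition. Mediation asks whether the arm shifts barriers and whether barriers track the outcome. Neither question, nor their product, requires the total effect to be significant. The indirect effect is also informative when the total effect is unclear. Section 2.1 reports such a pattern: in the one published evaluation of ATTOC, clinician beliefs and provision of nicotine replacement improved, while client tobacco use was not significantly lower. If this trial repeats that pattern, the plan as written leaves the indirect effect on quitting unestimated.

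The second is the level of analysis. Section 7.2.1 has barriers predicting client quit rates, but does not say which instrument serves which outcome. If a staff S-KAP score is used for client quitting, the only connection described between a staff member and a client is the clinic, and there are 14 clinics. Without a stated clinic level, an analyst could treat about 700 client records as that many independent values of the mediator.

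**Working it through.** **Inputs.** 14 clinics, 7 per arm (Section 4.1). About 280 staff and 700 clients (Section 5.2), so on average 20 staff and 50 clients per clinic. Aim 1 SD 0.87; usual-care quit rate below 2%, taken as 2%; ICC 0 to .15 (Section 7.1). Alpha .05 is taken as two-sided.

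**1. The plan's own figures.**

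Aim 1: detectable difference = (t.975,12 + t.80,12) × 0.87 × √[(2/140)(1 + 19·ICC)], with 2.179 + 0.873 = 3.052. This gives 0.317, 0.443, 0.540 and 0.623 at ICC 0, .05, .10 and .15, against 0.32, 0.44, 0.54 and 0.62 stated. A normal multiplier gives 0.291 at ICC 0 and does not match. The Aim 1 calculation therefore already counts clinics (14 − 2 = 12 df).

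Aim 2: 350 per arm with design effect 1 + 49·ICC and a pooled z test gives 4.2, 10.0, 14.9 and 19.4 points, against 4, 10, 15 and 19 stated.

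**2. How likely is the condition to be met?**

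For Aim 2 at one time point, SE = √{[0.02·0.98 + p(1−p)]/350 × (1 + 49·ICC)}, with power from the noncentral t on 12 df. The 13% ATTOC rate is the uncontrolled Connecticut figure in Section 2.2. The 8% rate is an assumption; 6% is 2% plus the plan's 4 points.

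| ICC | design effect | 2% v 6% | 2% v 8% | 2% v 13% |
|---|---|---|---|---|
| 0 | 1.00 | 0.70 | 0.92 | 1.00 |
| .05 | 3.45 | 0.27 | 0.44 | 0.80 |
| .10 | 5.90 | 0.18 | 0.29 | 0.57 |
| .15 | 8.35 | 0.14 | 0.22 | 0.44 |

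With a normal reference instead, Φ(difference/SE − 1.96), the 13% column at ICC .05, .10 and .15 becomes 0.86, 0.64 and 0.50 (ratios 3.04, 2.33, 1.96). The conclusion does not change.

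If both aims must succeed, multiply by the Aim 1 power. With an Aim 1 effect of 0.51 (the follow-up change quoted in Section 7.1) that power is 0.99, 0.90, 0.75 and 0.63. The joint chance with 2% v 13% is then 0.99, 0.71, 0.43 and 0.28. With an Aim 1 effect of 0.32 and 2% v 6% it is 0.57, 0.14, 0.07 and 0.04.

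**3. The staff-barrier-to-client-quit path.**

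There are 14 clinic values. With an intercept, arm and the mediator fitted, 14 − 3 = 11 df remain. Critical partial correlation = t/√(t² + 11) with t.975,11 = 2.201, which is 2.201/√15.84 = 0.553. For 80% power the true partial correlation must be about 0.71. If 700 clients were independent, a correlation of about 0.11 would do.

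**4. If clinic means were attached to clients with no clinic term.**

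The false-positive rate of a nominal 5% test is 2[1 − Φ(1.96/√(1 + 49·ICC))].

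| ICC | formula | simulated, individual level | simulated, clinic level (11 df) |
|---|---|---|---|
| .05 | 29% | 28% | 4.6–4.9% |
| .10 | 42% | 37–42% | 4.8–4.9% |
| .15 | 50% | 43–48% | 4.5–5.3% |

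The simulation used 5,000 runs per setting, 50 clients per clinic, overall quit rates of 5% and 10%, and a barrier unrelated to quitting.

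**5. The week-8 change score.** Section 7.2.1 uses mediator change to week 8. The schedule in Section 6 places S-KAP and S-KAS at baseline and weeks 12, 24, 36 and 52, and Section 6.2.3 has no study procedures in usual care at week 8. The score cannot be computed as written.

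**The case against.** The best case for the plan has four parts.

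- *The client mediator already exists.* S-KAS is named and scheduled as a mediator. A reader might infer that the whole aim rests on 14 points. It does not: client barriers to client quitting can use about 700 clients, and staff barriers to staff adherence about 280 staff. This stands. The 14-point limit covers only the staff-to-client cross path.
- *Only the partition is conditional.* A reader might infer that the trial could not show barriers moving without quitting following. The documents do not support that. The arm-to-barrier test carries no condition, and Aim 2 is reported whatever its result. What would be missing is the indirect effect and whether barrier change tracked quitting.
- *Clustering is promised in general.* A reader might infer that the plan will run a test with a 28–50% error rate. No section describes attaching clinic means to clients without a clinic term, and Section 7.2 argues against that reading. The rates show what the silence leaves open. The general promise still does not say how staff scores reach clients or what form the SEM takes.
- *The condition may be met.* Section 7.1 expects smoking rates to be more independent than provider adherence. At ICC 0 with 13% quitting under ATTOC, Aim 2 would almost surely succeed. This is fair, but the plan itself allows for ICCs up to .15.

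Showing a total effect before partitioning it is also a recognisable sequence, and the aim is exploratory.

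**Conclusion.** The point holds in limited form and is minor, since no primary or secondary conclusion depends on it. The condition is explicit and unnecessary. At ICC .05–.15, Aim 2 is met with probability 0.14 to 0.80 over the effects tried, and both aims with probability 0.04 to 0.71. The text does not define the demonstration required, or say whether the aims must succeed jointly or each outcome is treated separately. The SEM paragraph lacks a clinic level, and the staff-to-client path has 11 residual df with a critical partial correlation of about 0.55.

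Assumptions: equal cluster sizes, two-sided alpha, the same ICC for both aims, one time point per aim, and independence of the two results (positive correlation would raise the joint figures). That staff and clients are linked only by clinic is inferred from silence: no individual link is described.

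**What to change.** 1. Delete the condition. Report the arm-to-mediator, mediator-to-outcome and indirect effects with cluster-aware confidence intervals whatever Aims 1 and 2 show.
2. Name the mediator for each outcome: S-KAS, already collected, for client quitting, and S-KAP for staff adherence. Fit each in a multilevel model with a clinic random effect. If clinic-mean S-KAP is related to client quitting, analyse it on the 14 clinics and report it as descriptive.
3. Take mediator change to a visit at which both surveys are scheduled, such as week 12.

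This costs SAP wording and multilevel code, with no new data collection. The downside is wider intervals for an exploratory aim.
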